# Summary project

## 一、 Research Program

Project name	Comparison of clinical efficacy of golden microneedles and 1565nm non-ablative dot matrix laser in the treatment of eyelid pouches
Purpose of the Study	The purpose of this test is to compare the efficacy of golden microneedles and 1565nm non-ablative dot matrix laser in the treatment of eyelid pouches.
Type of study	Randomized, double-blind, self-controlled study
Number of cases	16
Inclusion and Exclusion Criteria	Inclusion Criteria: 

1. Patients with blepharoplasty;

2. Fitzpatrick III-V;

3. Males and females between 18-60 years old.

	Exclusion criteria: 

1. Other diseases that can cause pathological changes in periorbital soft tissue, such as collagen disease, kidney disease, liver cirrhosis, Graves disease, diabetes, scleroderma, hyperlipidemia, myasthenia gravis, Horner syndrome, myosermatitis etc;

2. Other diseases affecting wound healing, such as systemic diseases such as diabetes, heart disease, hypertension, infectious diseases such as tuberculosis, hepatitis, skin diseases, tumors, etc.; such as dry eye syndrome, cataract, glaucoma ophthalmic diseases.

3. Take steroids, vasodilators, anticoagulants (warfarin, non-steroidal anti-inflammatory drugs, aspirin, heparin, etc.) and retinoids 2 weeks before surgery. Local infections on the skin.

	
4. Patients with blepharoplasty, periorbital laser, botulinum toxin type A treatment history, and herpes simplex virus (HSV) infection history 6 months before surgery. History of exposure 2 months before surgery.
 
5. Scar physical, pregnancy, bilateral asymmetrical eye bags. Before entering the group, they were informed of their risks, benefits, and possible complications after the operation, and signed an informed consent.
 
6. Can not guarantee treatment on time, those who fail to cooperate.

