Treatment options	
16 patients with blepharoplasty bags, and two bilateral blepharoplasty bags were treated with laser respectively, and subjective adverse reactions (pain, burning, and burnout) were recorded before treatment, 4 weeks after each treatment, and 12 and 24 weeks after the third treatment. Itching, dryness), objective adverse reactions (erythema, pimples, edema, exudation, bleeding, scabbing, infection), patient satisfaction VAS score, visa skin tester, 3D skin test, ultrasound measurement of lower eyelid fat volume every 4 weeks Treat once and treat three times per person.

Efficacy evaluation	
Effectiveness evaluation indicators:
 
 
1. Patient satisfaction
 
2. Wrinkles, texture and pores by VISIA
 
3. 3D data changes
 
4. Ultrasound measurement of BLEs volume.
 
 
Safety evaluation indicators:
 
 
1. Subjective adverse reactions-pain, burning, itching, dryness
 
2. Objective adverse reactions-erythema, pimples, edema, exudation, bleeding, crusting, infection.
 

Statistical	
The pain of the left and right lower eyelids was tested by paired t

methods	test, the changes of various indexes of visia, 3D, and ultrasound were compared with the Wilcoxon symbol rank test of paired samples, and the subjective and objective adverse reactions were tested by $\chi^2$ test.
Study period	2 years

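### The χ² test for adverse reactions is not stated to be paired, and the pain contrast is written left versus right rather than device versus device, in a within-patient comparison of 16 patients

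*Combined protocol and SAP*

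**What the plan says.** All the relevant text is in section 一 (Research Program) of the combined protocol and SAP.

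- **Type of study:** "Randomized, double-blind, self-controlled study", with 16 cases.
- **Purpose:** to "compare the efficacy of golden microneedles and 1565nm non-ablative dot matrix laser".
- **Treatment options:** both lower-lid bags of each patient are treated *respectively*. Adverse reactions "were recorded before treatment, 4 weeks after each treatment, and 12 and 24 weeks after the third treatment". With three treatments, that is one pre-treatment and 3 + 2 = 5 post-treatment recordings.
- **Statistical methods:** three tests are named. For pain, "The pain of the left and right lower eyelids was tested by paired t" test. The VISIA, 3D and ultrasound changes are "compared with the Wilcoxon symbol rank test of paired samples". For the rest, "the subjective and objective adverse reactions were tested by" χ², with no qualifier.
- **Safety indicators:** the first item is "Subjective adverse reactions-pain, burning, itching, dryness", so pain belongs to the class sent to the χ² test as well as having a t test of its own.

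The plan does not expressly say that one eyelid gets each device. *Self-controlled*, *respectively* and a paired left/right test together make that the natural reading, and I adopt it.

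**The concern.** If each patient carries both devices, each yes/no adverse reaction yields 16 matched pairs, not two independent groups of 16 eyelids. The ordinary χ² test treats the 32 eyelids as independent. The plan marks pairing for two of its three tests and not for this one, so an analyst who follows the text could reasonably run the unpaired test.

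The pain test is paired, but on anatomical side. The question is microneedle versus laser. If the device on the left differs between patients, left minus right adds the device effect in some patients and subtracts it in others.

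Pain and the listed reactions make up the plan's whole safety comparison. What is at stake is whether that comparison has the error rate it claims and addresses the device difference.

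**Working it through.** The plan gives N = 16 without rates, correlations, effect sizes or power, so it has no figure to reproduce. Every rate, correlation and effect below is my assumption. Tests are two-sided at 5%, with one value per eyelid.

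**1. Adverse reactions: size.** For a common rate p and within-patient correlation ρ, the difference in proportions has variance 2p(1−p)(1−ρ)/16. The ordinary (Pearson) χ² uses 2p(1−p)/16. Its z statistic is therefore too small by a factor √(1−ρ). At ρ = 0.5 the effective cut-off is 1.96/0.707 = 2.77, a tail of about 0.6%. Exact enumeration of all 969 possible paired tables for n = 16, at p = 50%, gives:

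| ρ | Pearson size | McNemar size, uncorrected |
|---|---|---|
| 0 | 5.2% | 4.3% |
| 0.3 | 2.1% | 4.95% |
| 0.5 | 0.7% | 4.5% |

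Uncorrected McNemar is (b−c)²/(b+c), where b and c are the two discordant counts. Its largest size for discordance up to 50% is 5.0%.

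**2. Adverse reactions: power at 60% versus 30%.**

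| ρ | Pearson | McNemar, uncorrected | McNemar, exact |
|---|---|---|---|
| 0 | 41% | 35% | 25% |
| 0.3 | 39.2% | 50% | 30.5% |
| 0.5 | 36.6% | 71% | 33.7% |

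Six rate pairs were run (60/30, 30/10, 40/10, 50/20, 50/30, 20/5). Uncorrected McNemar has more power than Pearson in all six from ρ of about 0.15 upward. At ρ = 0 it has up to 7 points less (48% versus 55% at 40/10). Exact McNemar has less power than Pearson in all six at every feasible ρ run, 0 to 0.5.

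**3. One data set.** Suppose 9 versus 4 of 16 sides react. Pearson is (5/16)² / [(13/32)(19/32)(2/16)] = 3.24, p = 0.072, whatever the pairing. McNemar depends on the discordant split:

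| b vs c | (b−c)²/(b+c) | p, uncorrected | p, exact |
|---|---|---|---|
| 5 vs 0 | 25/5 = 5.00 | 0.025 | 0.0625 |
| 6 vs 1 | 25/7 = 3.57 | 0.059 | 0.125 |
| 7 vs 2 | 25/9 = 2.78 | 0.096 | 0.18 |

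**4. Pain.** Assume a true device effect of 0.75 SD of the paired difference. By device, the noncentrality is 0.75 × √16 = 3.0 on 15 df, with critical value 2.131 and power 80%. If k patients have the microneedle on the left, left minus right has expectation 0.75 × (2k−16)/16. At k = 8 that is zero, and the device effect becomes noise: the expected sample variance of the differences rises from 1 to 1 + 0.75² × 16/15 = 1.6. Simulated rejection (300,000 trials per setting):

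| Sides | Left minus right |
|---|---|
| 8/8 | 1.5% |
| Coin flip | 5% |
| 12/4 | 17% |
| 14/2 | 46% |
| Fixed side | 80% |

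With a fixed side, left versus right is the device contrast and nothing is lost.

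**The case against.** The strongest reply is that this is ambiguity in a translated summary table, not a demonstrated error. McNemar's test is itself a χ² test and may be what was meant. *Left and right* may be loose wording for the two treated sides. Analysts whose stated purpose is to compare devices would hardly ignore which device each side received. All of that is possible, and the figures above apply only to the literal reading. It does not remove the point, because the surviving text does not settle it and settling it is nearly free.

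A second reply is that the paired test need not do better. This stands for the exact version, and the example in step 3 crosses 5% only with 5 versus 0 under the uncorrected version. A reader might infer that pairing guarantees more power; the figures do not support that.

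A third reply is that a specific clause for pain followed by a general clause for adverse reactions is naturally read as the t test for pain and χ² for the rest. I agree, so the overlap is a minor clarification.

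Finally, the headline purpose is efficacy, and the instrument measures already have a paired test. The point therefore concerns the safety comparison only.

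**Conclusion.** The point holds in a limited form. As written, the adverse-reaction test is not stated to be paired, and the pain contrast is not stated by device. With one value per eyelid and positive correlation, the literal χ² is conservative (2.1% at ρ = 0.3 and 0.7% at ρ = 0.5, for 50% rates). The literal pain contrast has almost no ability to detect a 0.75 SD device effect when sides are balanced or assigned by coin flip. Both results rest on one device per eyelid, which is inferred, and the pain result also requires that device varies by side, which *Randomized* suggests but the available text does not state.

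Two stronger readings should be resisted. A reader might infer that the unpaired test inflates false positives. That would require pooling the repeated recordings as if independent, and the plan nowhere says it will. A reader might also infer that the plan fails to say how device is allocated to side. The research process section survives only as a heading here, so that text may simply not be in the available copy.

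This should be fixed, with medium confidence, since intent cannot be read from the text.

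**What to change.** Replace the pain and adverse-reaction clauses with wording to this effect:

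> All between-device comparisons are within patient, golden-microneedle side versus laser side, whichever eyelid that is. Before-after changes may also be analysed. Pain is compared by the paired t test on the device difference, using one prespecified value per eyelid that takes the pre-treatment recording into account, and is not also tested by χ². Each other adverse reaction is scored once per eyelid (new or worse than pre-treatment at any post-treatment recording, yes or no) and compared by McNemar's test, in a version named in advance. Both discordant counts and the exact p-value are reported.

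Keep the Wilcoxon clause. Record the device on each side for every patient, and state, or cross-refer to, how device is assigned to side.

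The cost is a few lines and no extra patients or visits. The choice of McNemar version is a real trade-off. The uncorrected version holds size at about 5% and has more power than Pearson from ρ of about 0.15, but up to 7 points less at ρ = 0. It is also approximate with few discordant patients: 4 versus 0 gives p = 0.046 against an exact 0.125. The exact version is valid but has less power than Pearson in every scenario run. Yes/no scoring drops grade and time course from the test; both can be described.

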## 二、 Research process
